8.3.2 QST

We will conduct appropriate statistical tests to compare the effects of stimulation (Burst-SCS and sham SCS) on the various QST measures. We will also look for potential correlations between pain intensity and QST measures.

9. STUDY SITES

We will conduct this study at UM, and therefore this is a single-center study. We will not perform this study at any UM Family Health Center, Regional Hospitals or any non-UM sites such as nursing homes, schools or community-based organizations.

10. INFORMED CONSENT

We will explain the study verbally and in writing. If interested, candidates will sign an informed consent, and will be given a copy. **We will withhold information regarding the type of treatment (active vs. sham), and the order of treatment (active/sham vs. sham/active) the subjects will receive during the study (concealment).** Instead, we will inform subjects that we are adjusting the settings on

their SCS device. We will inform candidates that the purpose of this study is to investigate the potential mechanisms of action of Burst-SCS. We will also explain to each candidate that there will be no expected benefit to him/her by participating in this research study. However, it is possible (although not anticipated) that during this research new stimulator settings may be found that could be beneficial. We will also explain that the knowledge gained from this research may be beneficial for others, society, and/or science. **Note:** We will debrief subjects at the conclusion of their last research visit (i.e. visit 5). Concealment is necessary to conduct this research study to avoid potential for altering subject behavior such that study results are biased.

The research team (e.g. PI or other study personnel) will conduct the consent interview and the interview will take place in a private setting (e.g. examination room, office), allowing sufficient time for prospective subjects to make an informed decision. Furthermore, we will also offer candidates the option of taking the informed consent form home to study and think about participation, with a follow up with one of the investigators or study personnel. We will only recruit subjects who can speak, read, and understand English.

11. WAIVER OR ALTERATION OF INFORMED CONSENT

Alteration of the informed consent is requested, since this research involves the deception or concealment of subjects.

12. CONFIDENTIALITY OF DATA

The study requires obtaining direct patient identifiers due to collecting standard of care data in addition to the research data for the project. We will assign subject numbers to patients and those numbers will be used in the research. We will maintain a password-protected file linking subject numbers to identifying information on a UM computer. Research personnel will store identified study data in accordance with standard regulations and will not be disclosed or shared with any outside third parties. Identifying information will be severed from study data that is reported. Only relevant research personnel listed in the institutional review board (IRB) study application will have access to study files and folders. We will protect the data on a laptop computer or on a removable device by encryption.

13. DATA SAFETY AND MONITORING

All research personnel involved in any way in this project will have completed training in the protection of human research participants per guidelines issued by the United States Department of Health and Human Services, Office for Human Research Protection. The protocol will undergo review and approval by the IRBMED and other necessary regulatory and oversight entities prior to implementation.

13.1 Causality

Events will be considered study related if classified by the PI or other study personnel as possible, probable, or definite. Association of events to the study will be made using the following definitions (**Table 2**).

Table 2. Definition of causality events.

Term	Definition
Definitely Not	The event is definitely not associated with the study
Probably Not	The temporal association, patient history, or clinical condition is such that the study is not likely to have had an association with the observed event.

Possible	The event: a) follows a reasonable temporal association with the study procedures, but b) could have been produced by the patient's clinical condition or other therapy.
Probable	The event: a) follows a reasonable temporal association with the study conduct, b) abates upon discontinuation of study procedures, and c) cannot be reasonably explained by the patient's clinical condition or other therapy.
Definite	The event: a) follows a reasonable temporal association with the study, b) abates upon discontinuation of study procedures, c) cannot be reasonably explained by the patient's clinical condition or other therapy, and d) reappears on re-exposure to the study procedures.
Unknown	Not enough information exists for the assessment of causality at the time of occurrence.

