13.3 Serious Adverse Event (SAE)

Any adverse event (AE) that:

- Is fatal;
- Is life threatening, meaning the patient was at immediate risk of death from the reaction as it occurred, i.e., it does not include a reaction that, had it occurred in a more serious form or progressed, might have caused death;
- Causes a persistent or significant disability or incapacity;
- Requires or prolongs inpatient hospitalization. Inpatient hospitalization will be considered a hospitalization if it is longer than 24 hours or requires an intervention to treat emergent symptomatology (non-diagnostic);

Other important medical events may be considered SAEs when, based upon appropriate medical judgment, they may jeopardize the patient and may require medical or surgical intervention to prevent one of the outcomes as listed in this definition. We will report SAEs to the IRBMED per the IRBMED Standard AE Reporting Plan at <https://az.research.umich.edu/file/864>. If the SAEs are not related to the study, we will report them at Continuing Review. If the SAEs are related to the study, we will report them within 7 days or sooner to the IRB. We will also report AEs and SAE's to the PI. If there is any evidence of a pattern of unanticipated AEs (regardless of causality), or SAE, we will immediately have an independent third party review these data. Based on the conclusions of this individual, the PI will either terminate the study or convene a Data Safety and Monitoring Board to make recommendations.

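### Table 2 has no category for a study event that does not abate and has no other explanation, so a fatal or irreversible SAE of that kind may miss the 7-day IRB report

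*Combined protocol and SAP*

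**What the plan says.** Section 13.1 defines relatedness by rating: "Events will be considered study related if classified by the PI or other study personnel as possible, probable, or definite". It says the ratings are assigned with the definitions in Table 2. The three related categories all begin with a reasonable temporal association and then differ:

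- *Possible*: "but b) could have been produced by the patient's clinical condition or other therapy".
- *Probable*: "b) abates upon discontinuation of study procedures, and c) cannot be reasonably explained by the" patient's condition or another therapy.
- *Definite*: the same abatement and no-other-explanation criteria as *Probable*, "and d) reappears on re-exposure to the study procedures".

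The remaining rows are *Definitely Not* (no association), *Probably Not* (an association is unlikely) and *Unknown* (too little information to judge).

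Section 13.3 lists four bulleted SAE criteria. One is a fatal outcome. Another reads "Causes a persistent or significant disability or incapacity". Related SAEs go to the IRB within 7 days or sooner. For the rest, "If the SAEs are not related to the study, we will report them at Continuing Review". Neither section waives abatement for events that cannot abate, gives a default for an event that fits no row, or says how an *Unknown* event is reported.

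**The concern.** Abatement on stopping is useful evidence of causation when an event is reversible. Table 2 makes it a necessary condition for both categories that apply when nothing else explains the event. A death cannot abate, and a permanent injury does not. The one related category without an abatement condition, *Possible*, is closed to such an event precisely because no other cause is available.

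This reverses the intended ordering. Between two irreversible events after study procedures, the one with a plausible alternative cause is study related, and the one with no alternative cause has no related category. At stake is prompt IRB reporting of the most serious kind of harm. The ratings are made by the PI or other study personnel, so consistent handling depends on the written definitions.

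**Working it through.** The plan gives no figure to reproduce. The check is a logical enumeration of Table 2 for an event with a reasonable temporal association.

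Inputs, all from Section 13.1, Table 2:

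- X = 1 if the patient's condition or another therapy could have produced, or can reasonably explain, the event; otherwise 0.
- A = 1 if the event abates when study procedures stop.
- R = 1 if it reappears on re-exposure.

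Rules: *Possible* = X. *Probable* = A and not X. *Definite* = A and not X and R.

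Assumption: the *Possible* wording (could have been produced) and the *Probable* wording (cannot be reasonably explained) are treated as complements, so one X serves both.

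| X | A | R | Related category met |
|---|---|---|---|
| 0 | 0 | 0 | none |
| 0 | 0 | 1 | none |
| 0 | 1 | 0 | Probable |
| 0 | 1 | 1 | Probable, Definite |
| 1 | 0 | 0 | Possible |
| 1 | 0 | 1 | Possible |
| 1 | 1 | 0 | Possible |
| 1 | 1 | 1 | Possible |

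Six of 8 combinations reach a related category. The 2 that do not are exactly those with X = 0 and A = 0.

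A death after study procedures has A = 0 and R = 0:

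- With X = 1 it is *Possible*, hence related, and is reported within 7 days.
- With X = 0 it meets none of the related categories.

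The X = 0 death does not fit the other rows either. *Definitely Not* and *Probably Not* deny or doubt an association that the facts support. *Unknown* needs a lack of information, and here the event may be fully documented. It is therefore unassigned.

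Effect of the proposed wording:

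- If abatement is not applicable to fatal or irreversible events, the X = 0 death or permanent injury becomes *Probable*.
- That change alone leaves one case open: an event with X = 0 that could abate but has not. The default rule (temporal association and no reasonable alternative explanation is at least *Probable*) covers it.
- With both changes, every X = 0 combination is at least *Probable* and every X = 1 combination is *Possible*, so 4 + 4 = 8 of 8 are related.

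**The case against.** The strongest case on the other side accepts the gap in the wording and disputes its consequences. Much of that stands.

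- **Routing.** A reader might infer that these SAEs are classed as not related and sent to Continuing Review. The documents do not say so. The event also fails *Probably Not* and *Definitely Not*, and Section 13.3 sends only unrelated SAEs to Continuing Review. A late report is a risk of literal use, not a stated outcome.
- **SAE criteria.** A reader might infer that two of the four bulleted criteria can never be rated *Probable* or *Definite*. That is too strong. The disability bullet covers persistent or significant disability, and a significant disability may abate. The gap covers fatal events and the irreversible part of other harms.
- **Named risks.** A reader might count the infection and device complications of Section 14.2.6 as falling in the gap. Usually they would not. Every subject is already in a standard-care trial of about 5-10 days, and Section 6.6 takes the active parameters from that care. Another therapy could have produced these events, so they would be *Possible* and related. The electrical burn in Section 14.2.4 is described as a minimal risk and may lessen once stimulation stops.
- **Safety analysis.** A reader might infer that the trial's safety result is understated. Section 8 defines no analysis of related adverse events, so the effect is on reporting.
- **Other controls.** Section 13.3 cites the IRB's standard reporting plan, which is not included and might require prompt reporting anyway. It also provides independent third-party review that does not depend on Table 2, and has AEs and SAEs reported to the PI. A sensible rater might choose a related category regardless.

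These points limit how often the gap matters. They do not close it. Rater judgement would mean departing from the definitions that the protocol tells raters to use. Third-party review is not the 7-day IRB report. The unseen reporting plan cannot correct the label in Table 2.

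**Conclusion.** The concern holds as a defect in the definitions. On the wording of Table 2, an event with a reasonable temporal association, no reasonable alternative explanation and no abatement fits no row, while the same event with a plausible alternative cause is study related. Because Section 13.3 makes the 7-day report depend on relatedness, an SAE of this kind may not be reported within 7 days.

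The gap is narrow: 2 of 8 logical combinations, in practice deaths and irreversible injuries with no other explanation. The number of affected events cannot be derived from the documents and is expected to be small with 20 patients.

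The conclusion assumes that Table 2 is applied literally and that the *Possible* and *Probable* wordings on alternative causes are complements. A rater who accepts any conceivable alternative as one that could have produced the event would reach *Possible* and avoid the gap. How the IRB's own reporting plan would treat an unassigned SAE is unknown from these documents.

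**What to change.** Make two changes in Table 2:

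1. In *Probable* and *Definite*, qualify the abatement criterion so that it applies where abatement can be assessed, and mark it not applicable to fatal or irreversible events.
2. Add a rule that an event with a reasonable temporal association and no reasonable alternative explanation is rated at least *Probable*, whether or not it resolves.

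Leave the re-exposure criterion of *Definite* as it is. Waiving it where no re-exposure took place would let the same event satisfy both *Probable* and *Definite*, and would not change relatedness, since both already count as related.

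The cost is a wording change to one table and possibly an occasional additional 7-day report. Treatment, visits, outcomes and sample size are unaffected.

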13.2 Severity

The PI or other study personnel will grade the signs and symptoms as mild, moderate, severe, or life threatening according to the following definitions (**Table 3**).

Table 3. Adverse events severity scale.

Grade	Definition
Mild	Causing no limitation of usual activity
Moderate	Causing some limitations of usual activities
Severe	Causing inability to carry out usual activities
Life Threatening	Patient was at immediate risk of death from the event

13.3 Serious Adverse Event (SAE)

Any adverse event (AE) that:

- Is fatal;
- Is life threatening, meaning the patient was at immediate risk of death from the reaction as it occurred, i.e., it does not include a reaction that, had it occurred in a more serious form or progressed, might have caused death;
- Causes a persistent or significant disability or incapacity;
- Requires or prolongs inpatient hospitalization. Inpatient hospitalization will be considered a hospitalization if it is longer than 24 hours or requires an intervention to treat emergent symptomatology (non-diagnostic);

Other important medical events may be considered SAEs when, based upon appropriate medical judgment, they may jeopardize the patient and may require medical or surgical intervention to prevent one of the outcomes as listed in this definition. We will report SAEs to the IRBMED per the IRBMED Standard AE Reporting Plan at <https://az.research.umich.edu/file/864>. If the SAEs are not related to the study, we will report them at Continuing Review. If the SAEs are related to the study, we will report them within 7 days or sooner to the IRB. We will also report AEs and SAE's to the PI. If there is any evidence of a pattern of unanticipated AEs (regardless of causality), or SAE, we will immediately have an independent third party review these data. Based on the conclusions of this individual, the PI will either terminate the study or convene a Data Safety and Monitoring Board to make recommendations.

13.4 Termination of Subjects

13.4.1 Subject Decision.

Subject participation is strictly voluntary and the research strictly knowledge driven; therefore, a subject may withdraw from further participation in the study without penalty or harm. Any reason(s) the subject may give for terminating his or her participation will be kept confidential. We will store the study documents according to the procedures outlined in the Confidentiality of Data section of this protocol (Section 12). We will require no further information of the subject and the subject will be compensated for their completed study visits prior to termination.

13.4.2 Investigator Decision.

Study personnel (PI, Co-Is, and study coordinator) will be authorized to release a subject from further study participation according to the following guidelines:

- The researcher believes that it is not in the subject's best interest to stay in the study.
- Subject becomes ineligible to participate.
- Subject's condition changes such that he or she needs treatment that is not allowed while taking part in the study.
- Subject does not follow instructions from the researchers.
- The study is suspended or canceled.

Upon termination of a subject, the investigators will ensure the subject is dismissed with any study documents to which he or she is entitled. Subjects will be compensated for their completed study visits prior to termination. Investigators will require no further obligation or participation from a terminated subject.

14. PROTECTION OF HUMAN SUBJECTS

14.1 Risks to Human Subjects

Potential risks include: risk related to Burst-SCS and lead placement, risk of completing surveys, risks related to QST, risks related to electrical stimulation, risk related to loss of confidentiality, and additional risks.

14.2 Potential Risks and Protection against Risk

14.2.1 Risk related to Burst-SCS therapy.

Subjects will be asked to sign a separate consent explaining the potential risks involved with Burst-SCS therapy by their own doctor(s) as part of their standard clinical care for chronic pain management.

14.2.2 Risk of completing surveys.

The risks associated with completing the personal symptom surveys, may cause some discomfort or personal distress. However, the subject may refuse to answer any question on the questionnaires or surveys that may be uncomfortable.

14.2.3 Risks related to QST.

The MAST testing may cause some temporary physical discomfort on the thumbnail. The MAST system includes multiple software, electrical, and mechanical safeguards to ensure that the amount of pressure applied does not exceed safe limits, including a safety release pin that the subject can turn to immediately release the pressure actuator from his or her thumb. The test is terminated at or before 10 kg/cm² of pressure which is a commonly-used maximum pressure level in human sensory testing and does not result in physical injury. Subjects can also stop the stimulus at any time or express instructions to stop the stimuli. The subjects can also withdraw their thumb from the device.

The vibrometer, pressure algometer and the pointed skin probe are commonly used in QST studies and will not cause any tissue injury at the maximum forces applied in this study. However, the instruments may cause minor physical discomfort in the areas of testing that is expected to resolve within minutes of test completion. We will halt these tests automatically if subjects report a pain rating of 100.

Overall, the QST procedures may cause minor but temporary physical discomfort. The comfort and well-being of the subjects are very important to us and we have designed the QST experiments following strict safety standards and to be as brief as possible. We will limit the intensity of each stimulus to levels that are deemed safe and acceptable. Furthermore, study personnel are trained by the investigators to be sensitive to participant discomfort and concerns. The patient can inform the person to stop the QST at any time that the pain or unpleasantness of the task becomes intolerable.

14.2.4 Risks related to electrical stimulation.

During the stimulator programming session, subjects will receive either 24 hours of clinically-effective Burst-SCS (i.e. active treatment phase) followed by 24 hours of sham SCS (i.e. no treatment phase/placebo control phase) or vice versa. For the active treatment phase, we will use clinically-effective stimulation parameters that provided the best pain relief as part of a patient's standard clinical care. Therefore, we do not anticipate any side-effects related to stimulation. However, stimulation-induced paresthesias may sometimes occur (usually as a tingling sensation) due to positional changes (e.g. bending, lifting) and/or extreme movement. We will instruct the subjects to avoid such movements during the 24-hour period. We will also ensure that we set the stimulation amplitude so that patients are unlikely to feel any stimulation-induced paresthesias. During the placebo control phase or no treatment phase of stimulation, we will use the same parameters as in the active treatment phase, except that we will set the stimulation amplitude to 0 mA. Therefore, patients may not get adequate pain relief, due to the absence of stimulation. To minimize this risk, we limit the duration of the placebo control phase to 24 hours.

Whenever using electricity to stimulate tissue, there is also the possibility of a shock hazard, including an electrical burn. However, we will use only electrical stimulators approved by the FDA for Burst-SCS. Therefore, the risk of tissue damage or electrical shock during the electrical stimulation is minimal.

14.2.5 Risks related to loss of confidentiality.

Physicians, engineers, and technicians participating in the necessary research procedures will each have initial access to the patient and his/her name. This is the case for any standard of care treatment. Collaborators in this research will acquire data that initially contains the patient's name and other identifiable information. However, we will assign subject numbers to patients and those numbers will be used in the research. We will maintain a password-protected file linking subject numbers to identifying information on a UM computer. Only relevant research personnel listed in the IRB study application will have access to study files and folders. We will protect the data on a laptop computer or on a removable device by encryption.

14.2.6 Additional risks

This research requires that subjects extend their Burst-SCS trial by an additional 2-3 days. This additional time may increase the likelihood of some risks, such as infection or other device-related complications. However, the total duration of the trial, including both the time for the standard of care (~5-10 days) and research procedures (~2-3 days), will be well within the 30-day trial period that is allowed for the approved indication of Burst-SCS. Therefore, the percentage chance that subjects incur these additional risks is negligible.

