2. SCHEDULE OF EVALUATIONS

	Screening/ enrollment visit	Pre- implantation visit ^a	First trial-phase visit	Second trial-phase visit	Third trial-phase visit
	Visit 1	Visit 2	Visit 3	Visit 4	Visit 5
Informed Consent	X				
Hospital Anxiety and Depression Scale (HADS)	X	X	X		
EQ-5D Health Questionnaire	X	X	X		
Demographics	X				
Concomitant Medications	X	X	X	X	X
Socio-demographics	X				
Brief Pain Inventory (BPI)	X	X	X	X	X
Coping Strategies Questionnaire (CSQ)	X	X	X	X	X
Michigan Body Map (MBM)	X	X	X	X	X
PainDETECT	X	X	X	X	X
Pain Disability Index (PDI)	X	X	X	X	X
Fibromyalgia Survey Questionnaire (FSQ)	X	X	X	X	X
Patient-Reported Outcomes Measurement Information System Sleep Disturbance Short Form Questionnaire (PROMIS-SD)	X	X	X	X	X
Short Form McGill Pain Questionnaire (SFMPQ)	X	X	X	X	X
Visual Analog Scale (VAS) – included in SFMPQ	X	X	X	X	X
Vitals (heartrate, blood pressure, respiration rate, blood temperature), height and weight	X	X	X	X	X
Multimodal Automated Sensory Test (MAST)	b	X	X	X	X
Vibrometer Test	b	X	X	X	X
Algometer Test	b	X	X	X	X
PinPrick Test	b	X	X	X	X
Conditioned Pain Modulation (CPM) Test	b	X	X	X	X
Randomization			c		
Treatment (Burst-SCS/Sham SCS)			d	X	X
Adverse Events	X	X	X	X	X

^aPre-implantation visit may also occur on the same day as the screening/enrollment visit

^bFamiliarization only

^cRandomization will occur at the end of Visit 3

^dTreatment will begin at the end of Visit 3

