6. PROPOSED STUDY METHODS

6.1 Study Design

The study design is a **randomized, double-blind, placebo-controlled, crossover study design**. Subjects will participate in up to five research visits (**Figure 1**). During the first visit, we will screen chronic pain patients who have already been selected to receive a temporary externalized trial of Burst-SCS from their own doctors as part of their standard clinical care. During the second visit, we will perform pre-operative baseline assessment in the subjects prior to implantation of their SCS electrode arrays. Following lead implantation, and during the externalized “**trial phase**” of Burst-SCS, we will randomize subjects to receive either 24 hours of clinically-effective Burst-SCS followed by 24 hours of sham SCS or vice versa (crossover design). We will perform assessments before the start of the

randomization (visit 3), and at the end of each 24-hour period (visits 4 and 5). **Note:** Empirical evidence suggests that maximal pain relief can be measured within 24 hours.³¹⁻³⁴ Patients also clearly state that their pain returns within a matter of seconds to a maximum of few hours when the stimulation is switched off.¹⁹ Therefore, the plan for the crossover to occur after 24 hours of the initial treatment should not only be sufficient to detect significant differences in pain relief, but should also allow sufficient wash-out time for the initial treatment. Furthermore, the 24-hour stimulation window will allow us to complete the experiment within a reasonable timeframe. On the contrary, increasing the crossover period to longer than 24 hours could lead to potential confounds, such as patients increasing their medications and/or patient withdrawal because sham SCS may not provide adequate pain relief.

[figure not shown]

Figure 1. Schematic of the study design. Testing time-points are denoted by *

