6.6 Stimulator programming

During the stimulator programming session, subjects will receive either 24 hours of clinically-effective Burst-SCS (i.e. active treatment phase) followed by 24 hours of sham SCS (i.e. no treatment phase/placebo control phase) or vice versa. Patients will be blinded during programming. Before patients participate in this study, clinicians will have determined which stimulation parameters provide the best pain relief as part of a patient's standard clinical care. For this study, we will use these clinically-effective stimulation parameters during the active treatment phase.¹⁴ During the placebo control phase or no treatment phase of stimulation, we will use the same parameters as in the active treatment phase, except that we will set the stimulation amplitude to 0 mA.¹⁴ We will use the **St Jude Medical™ Invisible Trial System** to apply stimulation via externalized extension wires (**this device is listed in section 16 of the IRB application**).^{14,15} Patients will not be able to change the stimulation settings during either treatment phase, as they will not receive the patient programmer. However, we will instruct patients to use the magnet, if needed, in the case of emergency. The magnet can be used to turn the stimulation on or off, in the absence of the programmer.

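### No adverse event check is scheduled at or after lead removal, although the plan says the research-added lead days may raise infection and device risk

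*Combined protocol and SAP*

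**What the plan says.** Section 14.2.6 states that the study adds 2-3 days to a standard externalized trial of about 5-10 days. It then says: "This additional time may increase the likelihood of some risks, such as infection or other device-related complications". The paragraph notes that the total remains inside the 30 days allowed for the indication and concludes: "Therefore, the percentage chance that subjects incur these additional risks is negligible".

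The schedule in section 2 has one row for safety, "Adverse Events X X X X X", one mark for each of visits 1 to 5. There is no later column. Section 6.1 caps participation: "Subjects will participate in up to five research visits". Section 10 treats visit 5 as the last research visit and places the debriefing at its end.

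On lead status, section 2 labels visit 5 the "Third trial-phase visit" and marks treatment there. Section 6.6 says the trial system is used "to apply stimulation via externalized extension wires". No section gives a date for lead removal.

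Section 13.1 grades causality, 13.2 severity, and 13.3 sets the reporting rules: related serious events go to the IRB within 7 days, and a serious event or a pattern of unanticipated events goes to an independent reviewer. None of these gives an end date for collection or a way of finding events after visit 5.

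**The concern.** The plan names a harm that its own extension may increase, then schedules no look for it once the extension is over. Infection and lead complications need not be evident while the leads are in use, so some may appear only at removal or later.

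Three things are at stake. First, the section 13 safeguards act only on events the team knows about; after visit 5 that knowledge depends on chance report. Second, a statement in the results that the extended trial phase had few or no complications could reflect when collection stopped. Third, the top two causality grades in section 13.1 (Probable and Definite) require that the event subsides once study procedures stop, and no scheduled contact follows that moment. Separately, the conclusion that the added risk is negligible rests on a comparison that does not address the added risk.

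**Working it through.** **1. Inputs.** Standard lead time about 5-10 days, research-added time 2-3 days, allowance 30 days (section 14.2.6). Two 24-hour periods, starting at the end of visit 3, with visits 4 and 5 falling "at the end of each 24-hour period (visits 4 and 5") (sections 2 and 6.1). Sample size 20 (section 8.1).

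**2. The plan's own figure.** Total lead time = standard + added: 5 + 2 = 7 days to 10 + 3 = 13 days. The margin to the allowance is 30 - 13 = 17 to 30 - 7 = 23 days. The statement that the total is well within 30 days reproduces.

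**3. Size of the increment.** Added time divided by standard time: 2/10 = 20%, 3/10 = 30%, 2/5 = 40%, 3/5 = 60%. As a share of total lead time, the added days are 2/12 = 17% to 3/8 = 38%. These are proportions of exposure time. The documents give no complication rate, so they do not convert to risk.

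**4. Does negligible follow?** The premise is that 7-13 is less than 30. The conclusion is about the difference in risk between, for example, 5 days and 8 days. An upper limit on total duration gives no information on that difference, and the same paragraph has just said that the difference may not be zero.

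**5. The observation window.**
- Visit 3 to visit 5: 24 + 24 = 48 hours, with adverse event checks at 24 and 48 hours.
- After visit 5: 0 scheduled days.
- At or after lead removal: 0 scheduled contacts.
- If the extension runs to 3 days, 3 - 2 = 1 day lies outside the interval from visit 3 to visit 5. The plan does not say on which side.

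That the leads are in use up to visit 5 is an inference from the visit label, the treatment mark and the externalized wires. It is the natural reading, but it is not stated.

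**6. The rules set beside the window.**

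| Rule | What it needs | Scheduled source after visit 5 |
|---|---|---|
| 13.1 Possible | plausible timing relative to study procedures | none |
| 13.1 Probable, Definite | also, the event subsides after procedures stop | none |
| 13.3 IRB report within 7 days | a known, related serious event | none |
| 13.3 independent review | a known serious event, or a pattern of unanticipated events | none |

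Subjects who withdraw are in the same position: section 13.4.1 asks nothing further of them.

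**The case against.** The strongest reply is that the safety rules do not stop at visit 5. Section 13.3 defines a serious event without any visit limit, and a lead infection found a week later could meet the timing criterion for at least Possible, which section 13.1 counts as study related. A reader might infer from the schedule that late events are outside the study's rules altogether. The documents do not support that. The gap is in finding such events, not in the reach of the rules.

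There are also informal routes. The trial phase is standard care under the patient's own doctors, the unblinded team may include the clinical care provider (section 6.5), and section 12 says standard-of-care data are collected. These make it likelier that a serious complication is heard of. None is described as adverse event follow-up, so they soften the gap without closing it.

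The absence is also only from the text available. Section 13.3 points to an institutional reporting plan that is not included, and the figure of the study design is not shown.

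Finally, the numbers are small. Purely as an assumption, take a total complication rate of 1% to 5% and risk proportional to lead time. Expected events due to the added days are then 20 x 0.01 x 2/12 = 0.03 to 20 x 0.05 x 3/8 = 0.38 over the whole study. This stands as a reason to keep the fix modest. It is not a reason to leave a named harm unobserved, and without follow-up the study cannot check whether its rates were that low.

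**Conclusion.** The point holds as a gap in ascertainment. Scheduled collection ends at visit 5, nothing is planned at or after lead removal, and the plan itself says the added days may increase infection or device complications. Later events would enter the section 13 rules only by spontaneous report, and a count of complications of the extended phase could be too low. By how much cannot be derived, because the documents give neither a complication rate nor onset times. The firm figures are 0 scheduled days after visit 5 and a 20% to 60% increase in lead time.

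Three further inferences should be avoided. Not every complication falls outside the window: one evident by visit 4 or 5 is collected. Infection and device problems are not the only burden the research adds: sections 14.2.2 to 14.2.4 also list survey distress, testing discomfort and inadequate relief during sham. And the 20% to 60% is time, not risk.

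The conclusion rests on the inference about lead status at visit 5 and on the absence of any follow-up in the text available. It does not touch the efficacy comparison.

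**What to change.** - Add two entries to the adverse event row in section 2: a check at lead removal, and one later telephone contact and/or chart check at a fixed date chosen by the sponsor. Ask specifically about infection, device problems and admissions.
- State in section 13 when adverse event collection ends, that 13.1 to 13.3 apply to events found at these contacts, and whether they also apply to subjects who withdraw after the extension begins.
- In section 14.2.6, replace the claim of negligible risk with a statement that lead time rises by about 20% to 60%, that the added risk is not quantified, and that it is monitored to the stated date.

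The cost is a short amendment, one check at removal and one brief later contact or chart check for each of 20 patients at a single site, by existing staff. The downside is a slightly later end of follow-up for the last patient. No treatment procedure changes.
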